1.3 Correlative Studies

With exception of the peripheral blood sample collected on Cycle 1 Day 4, all correlative studies will be collected under HRPO# 201011766 (“Tissue Acquisition for Analysis of Genetic Progression Factors in Hematologic Diseases”) that all patients will be concurrently enrolled in. The goals of the correlative studies include:

1. To correlate patient-specific mutations with response to decitabine.
We will perform exome sequencing of each patient’s pre-study bone marrow sample and skin sample. We will determine AML/MDS-associated variants found in the bone marrow, but not skin sample. We will correlate the presence of mutations with response (especially mutations in *DNMT3A*, *IDH1*, *IDH2*, and *TET2*). This study is powered to identify mutations with >80% sensitivity to predict decitabine response if used as a clinical assay.
2. To correlate the velocity and depth of response with response to decitabine.
We will assess tumor burden by allele frequency of patient-specific mutations in bone marrow samples collected pre study, Cycle 1 Day 10±1, Cycle 1 Day 28±4, and Cycle 2 Day 28±4. We will assess mutations in at least 24 recurrently mutated genes (including, but not limited to: *FLT3*, *DNMT3A*, *NPM1*, *TET2*, *WT1*, *IDH1*, *IDH2*, *RUNX1*, *NRAS*, *TP53*, *U2AF1*, *KRAS*, *PHF6*, *MSTP9*, *PTPN11*, *KIT*, *SMC3*, *PRUNE2*, *ETV6*, *CEBPA*, *SMC1A*, *ASXL1*, *STAG2*, *RAD21*) as well as all patient-

specific mutations discovered during exome sequencing. The leukemic allele frequency will be measured using the Illumina MySeq or HiSeq platform using DNA capture by gene specific biotinylated-oligonucleotides. Patient bone marrow samples will be assessed pre-study, Cycle 1 Day 10 \pm 1, Cycle 1 Day 28 \pm 4, and Cycle 2 Day 28 \pm 4 and compared with patient specific skin samples (normal control). The velocity of response will be calculated as the natural log rate of patient-specific mutation allele frequency clearance. Depth of response will be defined as the lowest patient-specific mutation allele frequency in a bone marrow sample. The velocity and depth of tumor response will be correlated to:

- Achievement of clinical CR,
- Time to best response,
- Mutational status,
- Time to disease progression.

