Because all patient-specific exome-discovered mutations will be assessed a second time in the primary bone marrow sample as well as the Cycle 1 Day 10 \pm 1, Cycle 1 Day 28 \pm 4, and Cycle 2 Day 28 \pm 4 bone marrow samples, this study will also serve to validate all exome-discovered mutations. This is important, because exome sequencing is associated with a 20-50% false-discovery rate depending on type I error tolerated (mutation-calling algorithms are typically set for greater sensitivity than specificity). Thus, many mutations discovered during exome sequencing are incorrect. This second analysis of these mutations will server to exclude these false positive calls.

3. To correlate the bone marrow expression profile from pre-study and Cycle 1 Day 10 \pm 1 with response to decitabine.

We will correlate expression signatures, and changes in expression signatures, with:

- Achievement of clinical CR,
- Mutation status.

4. To correlate steady-state plasma decitabine concentration on Cycle 1 Day 4 \pm 1 with:
 - Achievement of CR.

5. To correlate the extent of bone marrow DNA hypomethylation on Cycle 1 Day 10 \pm 1 with response to decitabine.

We will assess the percent reduction in bone marrow methylcytosine content using LC-MS. Patients will be evaluated pre-study and Cycle 1 Day 10 \pm 1. The change in DNA methylcytosine content will be correlated to:

- Achievement of clinical CR,
- Change in expression signature.

This will determine whether inadequate blast exposure to decitabine correlates with drug resistance.

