3.2 Exclusion Criteria

1. Patient must not be pregnant or nursing.
2. Patient must not have known CNS leukemia.
3. Patient must not have a history of positive HIV serology.
4. Patient must not have a history of positive Hepatitis C serology.
5. Patient must not have undergone a prior allogeneic stem cell transplant.
6. Patient must not have any uncontrolled intercurrent illness including, but not limited to, ongoing or active infection, ongoing or active GVHD, congestive heart failure of NYHA class 3 or 4, unstable angina pectoris, cardiac arrhythmia, or psychiatric illness/social situation that would limit compliance with study requirements.
7. Patient must not have had radiation therapy within 14 days of enrollment.
8. Patient must not have received any chemotherapy within 21 days of enrollment, and any acute treatment-related toxicities must have returned to baseline. Patients

may be receiving hydra at time of enrollment.

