5.4 Concomitant Therapy and Supportive Care Guidelines

5.4.1 Chemotherapy

Patients cannot receive any chemotherapy within 21 days of study enrollment and must have recovered from any treatment-related toxicities. However, patients may be receiving hydrea at enrollment and may continue on hydrea through Cycle 2 of decitabine. An indication for hydrea following 2 cycles of decitabine is evidence that the patient is not responding and decitabine should be discontinued. Other than decitabine, patients cannot receive chemotherapy during this trial.

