9.1 Response Criteria - AML

AML Patients will be assessed for response according to the IWG criteria:¹

Morphologic complete remission (CR) – Defined as morphologic leukemia-free state, defined as less than 5% blasts in aspirate with marrow spicules and a count of ≥ 200 nucleated cells and no blasts with Auer rods or any persistence of extramedullary disease. When erythroid precursors constitute less than 50% of bone marrow nucleated cells, the percentage of blasts is based on all nucleated cells; when there are 50% or more erythroid cells, the percentage blasts should be based on the nonerythroid cells. The presence of mild megaloblastoid changes may be permitted if they are thought to be consistent with treatment effect. However, persistence of pretreatment abnormalities (eg, pseudo-Pelger-Hüet cells, ringed sideroblasts, dysplastic megakaryocytes) are not consistent with CR. In addition, ANC $> 1000/\mu\text{l}$ and platelet count of $\geq 100,000/\mu\text{l}$. Patient must be independent of transfusions. No duration requirement for this designation.

Cytogenetic complete remission (CCR) – Defined as morphologic complete remission plus a reversion to a normal karyotype. For this study, reversion of a normal karyotype is defined as no clonal abnormalities detected in a minimum of 20 mitotic cells.

Morphologic complete remission with incomplete blood count recovery (CRi) – Defined as morphologic complete recovery with the exception of neutropenia $< 1000/\mu\text{l}$ or thrombocytopenia $< 100,000/\mu\text{l}$.

Partial remission (PR) – Defined as meeting the above criteria for complete remission, with the following exceptions: decrease of $\geq 50\%$ in the percentage of blast to 5-25% in the bone marrow aspirate. A value of $\leq 5\%$ blasts in bone marrow with Auer rods present may also be considered a partial remission.

Stable Disease (SD) – Defined as not meeting the definitions of CR, CRi, PR, PD, or recurrence/morphologic relapse.

Progressive disease (PD) – Defined as a clear increase in bone marrow blast count, typically a greater than 50% increase compared with baseline, or new extramedullary disease. Patients with a $> 50\%$ increase in peripheral blast count with an increase of the total peripheral white blood cell count to $> 10,000/\mu\text{l}$ should undergo evaluation by bone marrow biopsy to access for progressive disease.

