14.2.3 Secondary Endpoint Analyses

The overall response rate (CR/CRi/PR) and complete response rate (CR/CRi) will be compared with historical controls[2], and the 95% confidence intervals will be provided.

The rate of patient specific mutation clearance after 10, 28, and 56 days of therapy will be determined using an Illumina based platform. We will compare the rate of mutation clearance between the patients who achieve a CR/CRi after 4 cycles and those who do not. We anticipate that we will identify between 6 and 25 exonic SNVs per case (the range obtained with >200 AML samples sequenced to date with whole genome or exome sequencing), and that the expected 95% confidence

interval of the mean variant allele frequency will be $\pm 2.56\%$ and $\pm 1.25\%$, respectively, if we assume an anticipated standard deviation of 3.2% within the same clone. The change of tumor burden over time and its association with clinical response will be assessed using 2-way ANOVA for repeated measurement data, followed by the ad-hoc multiple comparisons for between-group differences (e.g., responders vs. non-responders) at given time points as well as the between-time differences within each group. The resultant critical P values will also be corrected using permutation analysis for multiple testing.

The steady-state plasma decitabine concentration on day 4 ± 1 will be measured and correlated with clinical overall response.

The percent decrease in bone marrow methylcytosine will be calculated on day 10 ± 1 . We will compare this reduction with previously published data and between the patients who achieve CR/CRi and those who do not. The correlation of peak plasma levels of decitabine with response will be assessed using 2-sample t-test or Mann-Whitney non-parametric rank-sum test as appropriate. The change of total bone marrow DNA methylcytosine from baseline and its association with both steady-state plasma drug levels and response will be assessed using 2-way ANOVA for repeated measurement data, followed by the ad-hoc multiple comparisons for between-group differences (e.g., responders vs. non-responders) and between-time differences. Similar analyses will be performed for the correlation of expression profiles and SNP analysis with pharmacokinetic data.

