15.0 DATA SUBMISSION SCHEDULE

Case Report Form	Submission Schedule
Original Consent Form	Prior to registration
Patient Registration Form Disease Diagnosis Form Inclusion Criteria Worksheet Exclusion Criteria Worksheet	Prior to starting treatment
Treatment Record Form	To be maintained throughout a patient's treatment cycle. The complete record is due at completion of treatment.
Bone Marrow Sample Collection Form	To be maintained throughout the course of the study at designated bone marrow sample collections time points (See Appendix 2).
Pathology: Bone Marrow Biopsy	To be completed upon the return of pathology report for each bone marrow biopsy.
Study Calendar Form	To be completed with the date of each time point upon occurrence.
Labs Form	To be completed upon the return of laboratory reports for each study time point (See Appendix 2)
Dose Modifications	To be maintained throughout the course of the study if dose modifications are performed.
Therapy Response Form	To be filled out upon remission (prior to, and/or on therapy)
End of Study Form	Due at the completion of the EOS visit, at the time of death, and/or at the time that the patient is lost to follow-up
Follow Up Form	
 • 30 days post date of last decitabine dose. • Every 6 months for 2 years after the last dose of study drug.
Record of Adverse Events	At the time of any AE

Any queries generated by Washington University must be responded to within 28 days of receipt by the participating site. The Washington University research team will conduct a regular review of data status at all secondary sites, with appropriate corrective action to be requested as needed.

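### Hydrea is permitted through Cycle 2, when every analysed on-treatment biomarker sample is taken, but no data item or secondary analysis names it, so it is an unmeasured potential confounder

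*Combined protocol and SAP*

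**What the plan says.** References are to the most recent version shown in the combined file, whose statistics are in Section 14.

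- **Permission.** Section 5.4.1: "patients may be receiving hydrea at enrollment and may continue on hydrea through Cycle 2 of decitabine". Exclusion Criteria 3.2 agrees that patients "may be receiving hydra at time of enrollment" (spelled that way). Section 5.4.1 continues: "An indication for hydrea following 2 cycles of decitabine is evidence that the patient is not responding and decitabine should be discontinued". Its closing sentence bars all chemotherapy except decitabine and does not mention the allowance just given.
- **Sampling.** Sections 1.3 and 14.2.3 place plasma at Cycle 1 Day 4, methylcytosine and expression change at Cycle 1 Day 10, and clearance at Days 10, 28 and 56. On clearance, 1.3 says: "The velocity of response will be calculated as the natural log rate of patient-specific mutation allele frequency clearance".
- **Analysis.** Section 14.2.3: "The change of tumor burden over time and its association with clinical response will be assessed using 2-way ANOVA" for repeated measurements. Drug levels are compared by t-test or rank-sum test. No covariate is named for any of these. The only planned adjustment is a logistic regression in 14.2.2, with the primary analysis, and its covariates are not listed.
- **Data capture.** The baseline list (5.2.2), the Day 1 list (5.2.3), the form list (15.0) and the flow chart (Appendix 2) contain no hydrea or concomitant-medication item. Transfusions, by contrast, are tracked throughout. The descriptive and safety analyses (14.2.1, 14.2.4) plan no concomitant-medication summary.

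**The concern.** A confounder must be linked both to the group and to the measurement. The plan itself suggests the first link: Section 5.4.1 reads an indication for hydrea after two cycles as evidence of non-response. Patients who need it during Cycles 1 and 2 may therefore be over-represented among non-responders.

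The second link is plausible but not documented. Section 5.4.1 deals with hydrea under chemotherapy. Section 1.2.2, readable only in an older version in the same file, says the 10-day course was designed to expose more blast divisions to decitabine. If a second drug changes how blasts divide during Days 1 to 10, it could change the demethylation or expression measured on Day 10.

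Section 1.3 says of the methylcytosine result: "This will determine whether inadequate blast exposure to decitabine correlates with drug resistance". If hydrea lowered demethylation and were commoner in non-responders, the data would show that pattern without any difference in decitabine exposure, and the bias would favour the study's hypothesis. For clearance the sign could go either way. The permutation correction in 14.2.3 deals with multiplicity and does not remove confounding. Without prospective dates and doses, the question may be hard to examine afterwards.

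**Working it through.** **1. Inputs.** From 14.2.3: 45 responders, 55 non-responders, SD of methylcytosine reduction 15 points, target difference 20 points, alpha 0.05 (taken as two-sided), stated power 99%. The documents give no hydrea share, no difference in use and no hydrea effect. Those below are assumptions.

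**2. The plan's own figure.** SE = 15 × √(1/45 + 1/55) = 3.02 points. Power for 20 points is above 99.9% by both the normal and the noncentral-t calculation, so the stated 99% reproduces. It assumes no confounding.

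**3. Bias from unadjusted hydrea.** Spurious difference = (difference in share using hydrea) × (shift in methylcytosine reduction due to hydrea). Assume use by 10–15% of responders and 40–50% of non-responders. The difference in use is then 40 − 15 = 25 to 50 − 10 = 40 percentage points. Assume a shift of 5 to 10 points. Rejection rate of a nominal 5% test when there is no true difference (normal approximation):

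| Use difference | Shift (points) | Spurious difference (points) | Rejection |
|---|---|---|---|
| 0.25 | 5 | 1.25 | 7.0% |
| 0.40 | 5 | 2.0 | 10.2% |
| 0.25 | 10 | 2.5 | 13.2% |
| 0.40 | 10 | 4.0 | 26.4% |

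The assumptions drive this. By noncentral t, a 0.10 use difference with a 10-point shift gives a bias of 1 point and 6.2% rejection; 0.30 with a 20-point shift gives 6 points and 50.4%.

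**4. Against the target.** The largest bias in the table is 4.0/20, one-fifth of the target. To produce all 20 points, the shift would have to be 20/0.40 = 50 points at a use difference of 0.40, or 20/0.25 = 80 points at 0.25.

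**5. Cost of a hydrea-free repeat.** On the shares in step 3, the number removed is 0.10 × 45 + 0.40 × 55 = 26.5 to 0.15 × 45 + 0.50 × 55 = 34.25, or about 27 to 34 of 100. Taking a wider range, with the same share removed from each group (noncentral t):

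| Share removed | n | Methylcytosine power | Cmax power |
|---|---|---|---|
| 0% | 45 vs 55 | >99.9% | 86.8% |
| 10% | 40 vs 50 | >99.9% | 83.0% |
| 20% | 36 vs 44 | >99.9% | 78.4% |
| 30% | 31 vs 38 | 99.97% | 72.1% |
| 50% | 22 vs 28 | 99.6% | 57.5% |

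Cmax (25 ng/ml, SD 40; stated power 85%, reproduced within tolerance) shows the loss for a smaller standardised difference: 25/40 = 0.63 SD, against 20/15 = 1.33 SD for methylcytosine. The plan's clearance power concerns variants within a clone and it gives no power for expression change. No bias was therefore quantified for either.

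**The case against.** The strongest reply is that this is a single-arm study of correlation and prediction, that every hydrea figure above is assumed, and that no passage says hydrea alters methylation, allele frequency or expression. All of that stands, and it limits the point to a potential confounder.

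A reader might infer more, and the documents do not support it:

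- **That all biomarkers are compromised.** The primary predictor is mutation status from the pre-study sample, a genotype that hydrea does not change. Day 4 plasma is a pharmacokinetic sample, and no hydrea effect on it is argued. Marrow from Cycles 4 and 6 falls after the window.
- **That hydrea is recorded nowhere.** No item is named for it, but form fields are not shown. Medical history or the "Treatment Record Form" could hold it. The file is also part 2 of 2, and the unseen part may contain a later version.
- **That adjustment is ruled out.** The logistic regression in 14.2.2 is open-ended. It leaves hydrea unspecified, and it does not cover the 14.2.3 comparisons.
- **That hydrea users are selected for high white counts.** This version sets no white-count threshold for hydrea; that wording is in superseded text.
- **That progression would be missed.** Section 9.1 calls for a marrow when peripheral blasts rise "with an increase of the total peripheral white blood cell count to" more than 10,000/µl, and hydrea could blunt that trigger. But marrows are scheduled at Day 28 of Cycles 1 and 2 in any case, so the effect is minor.
- **That effects cannot be attributed to decitabine at all.** Only some patients would take hydrea, and the claims in 1.3 are about correlation.

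One further objection stands and shapes the fix. Hydrea use later in Cycles 1 and 2 may be a consequence of early non-response, so conditioning on it can remove real signal or introduce selection.

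**Conclusion.** The point holds for the secondary analyses. A permitted drug, whose later need the plan reads as non-response, overlaps every analysed on-treatment sample, with no named data capture and no adjustment in the responder comparisons. It is an unmeasured potential confounder of clearance, demethylation and expression change. The primary analysis of baseline mutation status is not affected in this way.

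The magnitude is unknown. For methylcytosine, a difference in use of 25 to 40 percentage points and an effect of 5 to 10 points, both assumed, give 1.3 to 4.0 spurious points and 7% to 26% rejection at a nominal 5%. This could make a small difference look real. Under these assumptions it would not by itself produce the 20-point difference the study is powered to find.

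**What to change.** **Data.** Add hydrea start date, stop date and daily dose, from pre-study to the end of Cycle 2, to the Treatment Record Form. This is three fields on an existing form.

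**Analysis.** Keep the planned comparisons in 14.2.3 and add two sensitivity analyses:

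- (a) a regression of Day 10 methylcytosine change, expression change and clearance velocity on response, with hydrea exposure before the sample as a covariate. This is a separate model, because the planned t-test, rank-sum and SAM procedures do not simply take an extra term;
- (b) a repeat of each of these comparisons in patients with no hydrea before the sample.

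**Cost.** The hydrea-free repeat could lose roughly 10% to 50% of patients (assumed range). Methylcytosine power stays at 99.6% or more, but comparisons with smaller standardised differences would lose more. For Day 28 and Day 56 samples, hydrea may follow from early non-response, so those results should be read as sensitivity only.

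**Text.** The hydrea allowance in 5.4.1 and that section's closing sentence barring other chemotherapy must be reconciled. No change to who receives hydrea is proposed.

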5.4.2 Growth Factors

Erythroid growth factors should not be routinely administered to patients during the study.

Thrombopoietin receptor agonists should not be routinely administered to patients during the study.

Filgrastim (G-CSF) or sargramostim (GM-CSF) may be administered to patients with septic shock or febrile neutropenia at the discretion of the treating physician.

5.4.3 Transfusions

- *Packed red blood cells (RBCs) transfusion:*
RBC transfusions will be administered at the discretion of the treating physician.
- *Platelet transfusion:*
Platelet transfusions will be administered at the discretion of the treating physician

5.4.4 Prophylactic Antimicrobial Agents

Antimicrobial agents will be administered at the discretion of the treating physician. Common antimicrobial prophylaxis during cycles 1 and 2 include acyclovir, ciprofloxacin, and fluconazole.

5.4.5 Radiotherapy

Patients cannot receive radiotherapy within 14 days prior to study enrollment or while on study.

6.0 DOSE MODIFICATIONS

A criterion for discontinuation of the study is a delay of > 8 weeks between any two cycles.

6.1 Delay for Cytopenia or Infection

As cytopenias are a defining feature of AML and MDS, their presence alone does not generally warrant dose modifications or delays. Patients will receive four cycles of therapy without adjustment for any cytopenia. Following Cycle 4, dose modifications or delays for cytopenias will be made at the discretion of the investigator.

Patients with febrile neutropenia (temperature $\geq 38.5^\circ$ with ANC $< 1,000/\mu\text{l}$) or systemic infections should have treatment held until clinical resolution of the infection.

6.2 Delay for Organ Dysfunction

If renal dysfunction (creatinine ≥ 3 X institutional upper limit of normal) or hepatic dysfunction (bilirubin ≥ 2.5 mg/dl or ALT/AST ≥ 3 X institutional upper limit of normal) occurs, therapy may not resume until the abnormalities have resolved to below the limits stated above. If renal or hepatic dysfunction occurs during a treatment course, the next dose of decitabine should be held, and serum chemistries should be checked twice per week. Decitabine can be resumed at full dose when creatinine, bilirubin, ALT and AST are below the limits listed above.

For grade 3-4 non-hematologic toxicities related to decitabine, decitabine treatment should be delayed until recovery to baseline or to grade ≤ 1 . Decitabine may be reintroduced with a 50% dose reduction, or at full dose at the discretion of the investigator.

6.3 Modification in Dose or Schedule for Treatment Response

Once AML patients achieve morphologic complete remission with incomplete blood count recovery (CRi) or MDS patients achieve a marrow complete response (Marrow CR) as defined in Section 9.0, decitabine administration may be decreased to 20 mg/m²/day for ten consecutive days, and the cycles may be administered every 6 weeks to limit myelosuppressive toxicity, at the discretion of the treating physician. After two cycles at six week intervals, the dose may be reduced to 20 mg/m²/day for five consecutive days of treatment in six week intervals. If the patient meets the definition of CR with complete cytogenetic response as defined in Section 9.0, administration may further be decreased to three consecutive days per cycle at the discretion of the treating physician.

[Redacted]

[Redacted]

[Redacted]

[Redacted]

[Redacted]

[Redacted]

[Redacted]

[Redacted]

[Redacted]

[Redacted]

[Redacted]

[REDACTED]

[REDACTED]

[REDACTED]

